9.3 Duration of Treatment

The duration of treatment will be approximately 52 weeks, including follow-up. Pre-treatment screening assessments shall occur within 21 days before the start of treatment.

10 EFFICACY, PHARMACOKINETICS, IMMUNOGENICITY, AND SAFETY VARIABLES

The planned schedule of assessments is in [Section 8.1.1](#). The planned schedule of correlative assessments is in [Section 8.1.2](#).

10.1 Efficacy, Pharmacokinetics, Immunogenicity, and Safety Measurements Assessed

10.1.1 Efficacy Variables

The following methods will be used for assessing and recording efficacy.

10.1.1.1 Best Corrected Visual Acuity Assessment

- BCVA will be assessed at all visits by ETDRS and the following:
 - Mean change in BCVA
 - Percentage of subjects who lose <15 letters
 - Percentage of subjects who gain ≥ 15 letters

10.1.1.2 Central Foveal Thickness

- CFT will be assessed at all visits by OCT.

10.1.1.3 Morphological Changes in the Neovascular Membrane

- Changes in the size and/or number of intraretinal cystoid space (cysts), subretinal fluid, and retinal pigment epithelium detachments measured by qualitative morphology-based OCT data (in the study eye).

10.1.1.4 Choroidal Neovascularization

- Leakage and size from the choroidal neovascularization.

10.1.2 Pharmacokinetic Variables

10.1.2.1 Pharmacokinetic Assessment(s)

- One or more PK variables based on plasma concentration of ranibizumab (primarily expected C_{max}).

10.1.3 Immunogenicity Variables

- Immunogenicity (ie, anti-ranibizumab antibodies and NAb)

10.1.4 Safety Variables

10.1.4.1 Safety Assessments

- AEs, as detailed in the following section
- ISRs (including endophthalmitis, vitritis, and haemorrhage)
- Hematology and clinical chemistry (including analysis of alanine aminotransferase also known as serum glutamic-pyruvic transaminase [ALT/SGPT] and aspartate aminotransferase also known as serum glutamic-oxaloacetic transaminase [AST/SGOT] and creatinine) as detailed in the following section.

10.1.4.2 Adverse Events

Adverse Event Definition

An AE is defined as any untoward medical occurrence in a clinical study subject administered a medicinal product which does not necessarily have a causal relationship with this treatment. An AE can therefore be any unfavorable and unintended sign (including an abnormal laboratory finding), symptom, or disease temporally associated with the use of a medicinal (investigational) product, whether or not it is related to the medicinal (investigational) product. This includes an exacerbation of pre-existing conditions or events, intercurrent illnesses, drug interaction, or the significant worsening of the indication under investigation that is not recorded elsewhere in the eCRF under specific efficacy assessments. Anticipated fluctuations of pre-existing conditions, including the disease under study, that do not represent a clinically significant exacerbation or worsening need not be considered AEs.

It is the responsibility of the investigator to document all AEs that occur during the study. AEs will be elicited by asking the subject a nonleading question, for example, "Have you experienced any new or changed symptoms since we last asked/since your last visit?" AEs should be reported on the appropriate page of the eCRF.

Assessment of Severity

Each AE will be assigned a category by the investigator as follows:

Mild: An AE that is easily tolerated by the subject, causes minimal discomfort, and does not interfere with everyday activities.

Moderate: An AE that is sufficiently discomforting to interfere with normal everyday activities; intervention may be needed.

Severe: An AE that prevents normal everyday activities; treatment or other intervention usually needed.

If there is a change in severity of an AE, it must be recorded as a separate event.

Assessment of Causality

Every effort will be made by the investigator to assess the relationship of the AE, if any, to the study drug. Causality should be assessed using the categories presented in the following table:

Unrelated: Clinical event with an incompatible time relationship to study drug administration, and that could be explained by underlying disease or other drugs or chemicals or is incontrovertibly not related to the study drug.

Related: Clinical event with plausible time relationship to study drug administration, and that cannot be explained by concurrent disease or other drugs or chemicals.

Action Taken

The investigator will describe the action taken with the study treatment in the appropriate section of the eCRF, as follows:

- Dose not changed
- Study drug permanently withdrawn
- Study drug temporarily interrupted
- Not applicable
- Unknown

Other Specific Treatment of Adverse Events

The investigator will describe the other treatment(s) for the AE/SAE in the appropriate section of the eCRF, as follows:

- None
- Concomitant medication

- Other, specify.

Follow-up of Adverse Events

All investigators should follow up with subjects with AEs until the event is resolved or until, in the opinion of the investigator, the event is stabilized or determined to be chronic. Details of AE resolution must be documented in the eCRF.

Subjects should be followed up for 28 days (\pm 5 days) after receiving the last dose of study drug, and any AEs that occur during this time should be reported according to the procedures outlined above.

Documentation and Reporting of Adverse Events

AEs should be reported and documented in accordance with the procedures outlined below. All AEs occurring during the study (from the time of receiving written informed consent to 28 days [\pm 5 days] of receiving last dose of study drug) must be documented on the relevant eCRF pages. The following data should be documented for each AE:

- Description of the symptom event
- Classification of “serious” or “not serious”
- Severity
- Date of first occurrence and date of resolution (if applicable)
- Action taken
- Causal relationship
- Outcome of event (unknown, recovered, not yet recovered, recovered with sequelae, death [with date and cause reported])

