8.4.9.3 Thromboembolic Events

Although there was a low rate of arterial thromboembolic events (ATEs) observed in the Lucentis® clinical trials, there is a potential risk of ATEs following IVT use of VEGF inhibitors. Arterial thromboembolic events are defined as nonfatal stroke, nonfatal myocardial infarction, or vascular death (including deaths of unknown cause).

The ATE rate in the 3 controlled wAMD studies (AMD-1, AMD-2, and AMD-3) during the first year was 1.9% (17 of 874) in the combined group of patients treated with 0.3 mg or 0.5 mg Lucentis® compared with 1.1% (5 of 441) in patients from the control arms. In the second year of studies AMD-1 and AMD-2, the ATE rate was 2.6% (19 of 721) in the combined group of Lucentis®-treated patients compared with 2.9% (10 of 344) in patients from the control arms. In study AMD-4, the ATE rates observed in the 0.5 mg arms during the first and second year were similar to rates observed in studies AMD-1, AMD-2, and AMD-3.

In a pooled analysis of 2-year controlled studies (AMD-1, AMD-2, and a study of Lucentis® used adjunctively with verteporfin photodynamic therapy [PDT]), the stroke rate (including both ischemic and hemorrhagic stroke) was 2.7% (13 of 484) in patients treated with 0.5 mg Lucentis® compared to 1.1% (5 of 435) in patients in the control arms (odds ratio: 2.2 [95% CI: 0.8,7.1]).

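### The two adverse-event causality categories in section 10.1.4.2 are not exhaustive: an event with plausible timing and a possible other cause fits neither

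*Combined protocol and SAP*

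**What the plan says.** Under Assessment of Causality, section 10.1.4.2 tells the investigator: "Causality should be assessed using the categories presented in the following table". Two categories follow.

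- *Unrelated*, first limb: "Clinical event with an incompatible time relationship to study drug administration, and that could be explained by underlying disease or other drugs or chemicals". A second limb covers events that are beyond doubt not due to the drug.
- *Related*: "Clinical event with plausible time relationship to study drug administration, and that cannot be explained by concurrent disease or other drugs or chemicals".

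There is no third category such as possibly related. The documentation list later in 10.1.4.2 makes causal relationship an item to record for every AE. Two outputs use it: the Synopsis (safety data) tabulates TEAEs by relationship to treatment, and section 11.3.4.1 plans a separate summary of treatment-related TEAEs.

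The AE definition in the same section is broad: "This includes an exacerbation of pre-existing conditions or events, intercurrent illnesses, drug interaction, or the significant worsening of the indication under investigation". That sentence goes on to limit the last item to worsening not already captured in the eCRF as an efficacy assessment. Only exacerbations of other pre-existing conditions and intercurrent illnesses are relied on below.

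**The concern.** A two-category label works only if every event falls into exactly one category. Here the two definitions are not complements. *Related* asks for plausible timing and the absence of any other explanation. *Unrelated* asks for incompatible timing and the presence of another explanation, or for certainty. The common case between them has no home: the timing fits, another cause is possible, and nobody can be sure.

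This case will arise often in practice. Subjects are aged 50 or over and are injected every 4 weeks, so many events will occur within weeks of a dose. An exacerbation of a pre-existing condition or an intercurrent illness usually has another candidate cause.

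Two consequences follow. First, each site must settle the matter for itself. Section 8.3.1 anticipates about 160 sites, or 580/160 = 3.6 subjects per site on average, so similar events may be labelled differently. Second, an investigator who follows the wording of *Related* literally must withhold that label from any event with another explanation, even when a drug contribution is quite possible.

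**Working it through.** There is no plan figure to reproduce. The check is a truth table on three attributes taken from the two definitions in section 10.1.4.2:

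- timing: plausible or incompatible;
- other explanation (disease, other drug or chemical): possible or none;
- incontrovertibly not related: yes or no.

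Underlying disease (in *Unrelated*) and concurrent disease (in *Related*) are treated as the same thing.

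*Related* = plausible AND no other explanation.

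The scope of the *or* in *Unrelated* is ambiguous, so both readings were tried:

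- Reading A = (incompatible AND other explanation) OR incontrovertible.
- Reading B = incompatible AND (other explanation OR incontrovertible).

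| Timing | Other explanation | Incontrovertibly not related | Related | Unrelated, A | Unrelated, B |
|---|---|---|---|---|---|
| plausible | possible | no | no | no | no |
| plausible | possible | yes | no | yes | no |
| plausible | none | no | yes | no | no |
| plausible | none | yes | yes | yes | no |
| incompatible | possible | no | no | yes | yes |
| incompatible | possible | yes | no | yes | yes |
| incompatible | none | no | no | no | no |
| incompatible | none | yes | no | yes | yes |

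The first row is the point: no category applies under either reading. The seventh row is also empty under both readings, but it should be uncommon. The second row is *Unrelated* under reading A and unclassified under reading B, so the *or* matters only once the investigator is certain. The fourth row, which is both *Related* and *Unrelated* under reading A, is close to self-contradictory and has little practical weight.

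Next, a search for a default. None is stated in the Synopsis safety text, in the documentation list of 10.1.4.2, in 10.1.4.2.1 or 10.1.4.2.2, or in 11.3.4.1.

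Finally, the reach of the label:

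- Affected: the tabulation by relationship (Synopsis) and the treatment-related TEAE summary (11.3.4.1), both descriptive.
- Not affected: the Week 8 BCVA equivalence analysis; TEAE tables regardless of cause; serious TEAE tables; and SAE reporting by the investigator, which 10.1.4.2.1 requires whatever the causality.

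The share of TEAEs in the empty cell would be needed to size the effect. Neither that share nor the label that sites would choose can be derived from the documents.

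**The case against.** The strongest reply is that investigators exercise judgement. With only two boxes available they will tick the nearer one, so no event goes unlabelled. That is probably right, and it is why the problem is inconsistent labelling and not missing data. It does not remove the problem, because the text directs investigators to these categories and neither one fits.

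A default may exist elsewhere. Section 11.1 defers technical detail to an SAP, and note 14 to the schedule in 8.1.1 mentions CRF completion guidelines. No separate SAP text and no guidelines were in the file reviewed. This stands as a caveat, although an SAP rule for missing causality would not repair the wording that investigators read. Section 10.1.4.2 calls the list a table, so a row lost in PDF extraction cannot be wholly excluded, but nothing in the text suggests one.

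The effect is also small. No test uses the label, and research staff other than those preparing and giving injections are masked (8.4.6), so much of the mislabelling should be similar in the two arms. That stands too, although similar mislabelling in both arms can still blur a difference.

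A reader might infer more than the documents support:

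- *That a known class risk is hidden.* Section 8.4.9.3 states that "there is a potential risk of ATEs following IVT use of VEGF inhibitors" and also reports such events in control arms. One could multiply the first-year rate by the arm size (290 x 17/874 = 5.6 events). That counts thromboembolic events, not events in the empty cell, and the rate pools 0.3 mg and 0.5 mg. Having vascular disease is also not the same as the event being explained by it. Stroke, myocardial infarction and vascular death would usually be SAEs, which are reported regardless of causality.
- *That expedited reporting is compromised.* Section 10.1.4.2.2 uses the word related but does not refer to the categories in 10.1.4.2, so the link is not established.
- *That worsening of wAMD falls in the gap.* The AE definition excludes worsening recorded under efficacy assessments, and it says that anticipated fluctuations of the disease need not be AEs.

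**Conclusion.** The point holds as a wording defect. As written, the two definitions leave an ordinary type of event without a category, and the reviewed text gives no rule for it. The consequence is possible between-site variation in a label that feeds two descriptive safety outputs. Its size and direction are unknown and cannot be calculated from the documents.

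The conclusion assumes that the two categories shown are the full list and that no default is given in the SAP or the CRF completion guidelines. It is a minor correction to a data-collection definition. It is not an error in the choice of analysis, and it gives no reason to doubt the equivalence conclusion, the all-causality safety comparison or SAE capture.

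**What to change.** In section 10.1.4.2, replace the two definitions with a mutually exclusive and exhaustive pair, for example:

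- *Related*: there is a reasonable possibility that the study drug contributed, even if another cause is also possible.
- *Unrelated*: there is no reasonable possibility that it contributed.

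At minimum, keep the present wording and add one sentence stating which category applies when timing is plausible and another cause is possible. Use the same words in the CRF completion guidelines, and footnote the treatment-related TEAE table with the date of the change.

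The new wording still rests on judgement, so some variation between sites will remain, but no event is left without a category.

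The cost is a protocol amendment with IEC/IRB approval (section 14.1) in about 15 countries and a notice to sites. It does not justify an amendment of its own and can be bundled with the next one. The number of events labelled *Related* may rise in both arms, and events recorded before and after the change will sit in one table under two wordings, which is why the footnote is needed.

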10.1.4.2.1 Serious Adverse Events

Serious Adverse Event Definition

An SAE is any untoward medical occurrence or effect that, at any dose,

- Results in death.
- Is life-threatening (an AE is life-threatening if the subject was at immediate risk of death from the event as it occurred, ie, it does not include a reaction that might have caused death if it had occurred in a more serious form).
- Requires or prolongs inpatient hospitalization. (Complications occurring during hospitalization are AEs and [are] SAEs if they cause prolongation of the current hospitalization. Hospitalization for elective treatment of a pre-existing non-worsening condition is not, however, considered an AE. The details of such hospitalizations must be recorded on the medical history or PE page of the eCRF).

- Results in persistent or significant disability/incapacity. (An AE is incapacitating or disabling if it results in a substantial and/or permanent disruption of the subject's ability to carry out normal life functions).
- Results in a congenital anomaly/birth defect.

In addition, medical and scientific judgement is required to decide if prompt notification is required in situations other than those defined for SAEs above. This may include any event that the investigator regards as serious that did not strictly meet the criteria above but may have jeopardized the subject or required intervention to prevent one of the outcomes listed above, or that would suggest any significant hazard, contraindication, side effect, or precaution that may be associated with the use of the investigational product.

Reporting of Serious Adverse Events

Any SAE must be reported by the investigator if it occurs during the clinical study, from the time of receiving written informed consent to 28 days (\pm 5 days) of receiving last dose of study drug, whether or not the SAE is considered to be related to the investigational product. All SAEs must be reported by the investigator within 24 hours of becoming aware of the SAE. An SAE report consists of the SAE form, the medical history form, and the concomitant medication form. A copy of these forms must be sent **within 24 hours** of becoming aware to the attention of the product safety scientist at:

[contact]
e-mail: [contact]

The investigator should not wait to receive additional information to document fully the event before notification of an SAE, though additional information may be requested. Where applicable, information from relevant laboratory results, hospital case records, and autopsy reports should be obtained.

Instances of death, congenital abnormality, or an event that is of such clinical concern as to influence the overall assessment of safety, if brought to the attention of the investigator at any time after cessation of study drug administration and linked by the investigator to this study, should be reported to the study monitor.

The Sponsor and/or Syneos Health will promptly notify all relevant investigators and the regulatory authorities of findings that could adversely affect the safety of subjects or the conduct of the study or alter the independent ethics committee (IEC)/institutional review board (IRB) approval/favorable opinion of the study. In addition, Syneos Health, on behalf of the Sponsor, will expedite the reporting to all concerned investigators, to the IECs/IRBs, where required, and to the regulatory authorities of all adverse reactions that are both serious and unexpected.

Details of the procedures to be followed if a pregnancy occurs are provided as follows.

Pregnancy Reporting

Pregnancies occurring in female subjects and female partners of male subjects during the study (from the time of first dose of study drug to 3 months after the last dose of study drug) should be reported by the investigator using the Pregnancy Report Form via email and fax ([Section 10.1.4.2.1](#)) immediately or within 24 hours of acknowledgement.

The investigator will (1) notify the subject's physician that the subject was being treated with an investigational drug (Xlucane) or approved control (Lucentis®/ranibizumab) and (2) follow the progress of the pregnancy. The investigator must document the outcome of the pregnancy and provide a copy of the documentation to the Sponsor.

If a female partner of a male study subject becomes pregnant during the study, the investigator will also notify the Sponsor immediately after the pregnancy is confirmed. The investigator will (1) obtain a consent from the female partner for pregnancy follow-up and (2) follow the progress of the pregnancy to term. The investigator should document the outcome of the pregnancy and provide a copy of the documentation to the Sponsor.

Any pregnancy will be followed to term and the status of mother and child will also be reported to the Sponsor after delivery. Newborns should be followed up for at least 30 days for any potential congenital anomalies.

Any SAE experienced during pregnancy must be reported on the SAE Report Form. Spontaneous abortions should always be reported as SAEs.

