8.4.9.1 Endophthalmitis and Retinal Detachments

IVT injections, including those with Lucentis®, have been associated with endophthalmitis and retinal detachments. Proper aseptic injection technique should always be used when administering study medication. In addition, patients should be monitored following the injection to permit early treatment should an infection occur.

Subjects should also be advised that in the days following study medication administration, they are at risk of developing endophthalmitis. If the eye becomes red, sensitive to light, painful, or develops a change in vision, advise the subject to seek immediate care from the local investigator (ie, an ophthalmologist).

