10.1.4.2.2 Unexpected Adverse Reactions

Unexpected Adverse Reaction Definition

An unexpected adverse reaction is any untoward and unintended response that is related to the administration of the study drug at any dose that is not consistent with the applicable product information (eg, investigator's brochure for an unauthorized investigational medicinal product or summary of product characteristics for an authorized product).

All suspected unexpected serious adverse reactions (SUSARs) will be the subject of expedited reporting. The Sponsor and/or Syneos Health shall ensure that all relevant information about a SUSAR that is fatal or life-threatening is reported to the relevant competent authorities and IEC/IRB within 7 days after knowledge by the Sponsor of such a case and that relevant follow-up information is communicated within an additional 8 days. All other SUSARs will be reported to the relevant competent authorities and IEC/IRB within 15 days after knowledge by the Sponsor of such a case. All investigators should follow up SUSARs until the event is resolved or until, in the opinion of the investigator, the event is stabilized or determined to be chronic. Post

study SUSARs that occur after the subject has completed the clinical study must be reported by the investigator to the Sponsor.

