11.3.4 Safety Endpoints

11.3.4.1 Adverse Events

Events that occur after a patient provides informed consent but before the time of the first dose of study drug will be considered non-treatment-emergent adverse events (AEs). Treatment-emergent AEs (TEAEs) are defined as events that are newly occurring or worsening from the time of the first dose of study drug.

Reported AE terms will be coded using Medical Dictionary for Regulatory Activities (MedDRA) preferred terms and system organ classes (SOCs).

The percentage of patients with TEAEs together with the number of the respective TEAEs overall, by SOC, and by preferred terms within each SOC will be presented. Separate summaries will be provided for overall TEAEs, TEAEs by severity,

treatment-related TEAEs, serious TEAEs, and TEAEs leading to treatment discontinuation.

All AEs will be presented in patient listings.

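### Section 10.1.4.2.1 does not make jeopardy to the subject or need for intervention a seriousness criterion, so endophthalmitis or retinal detachment treated without admission can be classified differently across sites and miss mandatory 24-hour reporting

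*Combined protocol and SAP*

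**What the plan says.** Under its SAE definition, Section 10.1.4.2.1 lists five criteria: death, threat to life, inpatient hospitalisation, disability and congenital anomaly. The two most relevant to an eye event are "Requires or prolongs inpatient hospitalization" and "Results in persistent or significant disability/incapacity".

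A further paragraph under the same definition says that "medical and scientific judgement is required to decide if prompt notification is required in situations other than those defined for SAEs above". The situations it may cover include "any event that the investigator regards as serious that did not strictly meet the criteria above but may have jeopardized the subject", events that needed intervention to avert a listed outcome, and events that point to a significant hazard of the product. No sentence says that any of these is an SAE.

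Other provisions depend on the serious label or bear on it:

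- Section 10.1.4.2.1 requires the investigator to report every SAE within 24 hours of becoming aware of it.
- Section 10.1.4.2 has each AE recorded in the eCRF as serious or not serious.
- Section 10.1.4.2.2: "All suspected unexpected serious adverse reactions (SUSARs) will be the subject of expedited reporting".
- Section 11.3.4.1 plans separate summaries that include "treatment-related TEAEs, serious TEAEs, and TEAEs leading to treatment discontinuation".
- Section 8.4.9.1: "IVT injections, including those with Lucentis®, have been associated with endophthalmitis and retinal detachments".
- The only event type designated as always serious is in the pregnancy part of Section 10.1.4.2.1: "Spontaneous abortions should always be reported as SAEs".

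**The concern.** The jeopardy-or-intervention clause is written as a judgement about notifying something that is not an SAE. It is not written as a criterion that makes the event an SAE. The protocol's own named injection risks fall into this class when they are treated on an outpatient basis and leave no lasting disability. Their seriousness can then turn on local admission practice and on individual reading of the clause, at about 160 sites in about 15 countries (Section 8.3.1).

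What is at stake is prompt and consistent safety information. Section 6.2.3 says that the product has had no earlier clinical study. Section 10.2 leaves a decision to terminate for safety to the sponsor and the contract research organisation, without a numerical threshold, so they rely on events reaching them quickly.

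**Working it through.** The protocol states no figure on this point, so the check is mainly a reading of the text.

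**Step 1. Does a sight-threatening event treated as an outpatient meet a listed criterion?**

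| Criterion (Section 10.1.4.2.1) | Endophthalmitis or retinal detachment, no admission, vision recovered |
|---|---|
| Death | Not met |
| Life-threatening, defined as immediate risk of death | Not met; risk to sight is not risk to life |
| Hospitalisation, inpatient only | Not met |
| Disability, defined by substantial or permanent disruption of normal life functions | Not met if vision recovers; can be met if loss persists, though this may be known only later |
| Congenital anomaly | Not applicable |

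The event is left to the additional paragraph.

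**Step 2. Does that paragraph make it an SAE?** It separates these situations from the defined SAEs, and the only decision it calls for is about prompt notification. It does mention events that the investigator regards as serious, and the eCRF has a seriousness field. Marking the event serious is therefore open to the investigator, but not required.

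**Step 3. What follows from the label?**

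- *24-hour report:* required for SAEs. A site following the text exactly need not send one for the event in Step 1.
- *Serious-TEAE summary:* the event is absent if it is marked not serious. The summary is descriptive.
- *Expedited reporting:* Sections 10.1.4.2.1 and 10.1.4.2.2 require the reaction to be unexpected as well as serious, judged against product information. Section 8.4.9.1 presents both events as recognised risks. The investigator's brochure is not among the documents, so expectedness for Xlucane cannot be settled.
- *Other summaries:* Section 10.1.4.1 counts endophthalmitis as an injection site reaction, and Section 11.3.4.2 summarises such reactions whatever their seriousness. Retinal detachment is not named there. Both events appear in the overall TEAE tables by system organ class and preferred term.

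**Step 4. Order of magnitude.** Planned injections: 580 subjects × 13 doses = 7,540. This is an upper figure, because it assumes no missed dose or dropout. The documents give no event rate per injection, so the following endophthalmitis rates are assumptions:

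- 7,540 × 0.0002 = 1.5 cases
- 7,540 × 0.0005 = 3.8 cases
- 7,540 × 0.001 = 7.5 cases

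These are totals for both arms. As an illustration, suppose four cases split two and two. If one case in one arm were marked not serious, the summary would show two against one. This shows how sensitive small counts are; it does not predict a bias.

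**The case against.** The strongest reply is that the text is ambiguous and does not exclude these events. The paragraph stands under the SAE definition, is introduced as an addition to it, and speaks of events that the investigator regards as serious. Every AE must be classified, so an investigator who thinks an endophthalmitis serious has a clear way to say so. This stands, and it limits the point: the protocol permits the right classification but does not require it. The 24-hour duty then depends on how each site reads the paragraph.

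Three stronger readings are tempting, and the documents do not support them.

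- *Expedited reports would be lost.* A reader might infer this because SUSAR reporting depends on seriousness. It depends on unexpectedness too, and both events are named as known risks.
- *The ocular safety comparison would fail.* Endophthalmitis, vitritis and haemorrhage are a separate safety endpoint, and all TEAEs are tabulated. Only the serious-TEAE table is exposed, and no test or decision rule rests on it.
- *The arms would be classified differently.* Randomisation is stratified by geographical region in permuted blocks (Section 8.4.3), so regional admission habits should fall about equally on both arms. Section 8.4.6 has an unmasked injector make the safety assessments immediately after injection, but the documents do not say that this person assigns seriousness.

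Nor is the spontaneous-abortion rule pointless in subjects aged 50 or older: pregnancy reporting also covers female partners of male subjects. It shows only that the protocol designates an event type as always serious when it chooses to.

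**Conclusion.** The point holds as a cheap improvement to safety reporting. As written, Section 10.1.4.2.1 does not oblige a site to report within 24 hours an endophthalmitis or retinal detachment that was treated without admission and left no lasting disability. The same event can be serious at one site and not at another.

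The effect is confined to mandatory prompt reporting and to one descriptive table. On the assumed rates, it concerns a handful of endophthalmitis cases at most. Any effect on expedited reporting is conditional on unexpectedness and stays open. The equivalence analysis, its power and its error rate are not affected.

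**What to change.** In Section 10.1.4.2.1:

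1. Add a sixth SAE criterion: an event that, in the investigator's medical judgement, jeopardises the subject or requires intervention to prevent one of the listed outcomes is an SAE, is recorded as serious in the eCRF, and is reported within 24 hours.
2. State that endophthalmitis and retinal detachment, already named as risks in Section 8.4.9.1, are reported under this criterion whether or not the subject is admitted.
3. Reword the additional paragraph so that judgement on prompt notification remains for its last limb, on significant hazards, contraindications, side effects and precautions. Simply deleting the reference to situations outside the SAE definition would leave the sentence incomplete and that limb without an anchor.

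Align the eCRF completion guidelines with the new text. The cost is protocol and guideline wording and a few more SAE forms. The drawback is a slightly higher SAE count in both arms. No treatment, endpoint or analysis changes.
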